7.4.4 Treatment duration

Patients will continue dosing of both study drugs (rogaratinib and atezolizumab) until any of the following occurs:

- Radiological disease progression according to RECIST v1.1
 - At the investigator discretion, study treatment may continue beyond radiological progression as defined by RECIST v1.1 (e.g. in case of suspected pseudoprogression) if the clinical condition of the patient is stable or the patient is improving symptomatically, and the investigator expects continued clinical benefit for the patient.
- Clinical progression
- Unacceptable toxicity
- Death
- Consent withdrawal
- Withdrawal from the study treatment at the discretion of the investigator or designated associate(s).

For full list of withdrawal criteria refer to Section 6.4.1.3.

23 MAY 2023 Version 6.0 Page: 81 of 181

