- Absence of symptoms and signs indicating unequivocal progression of disease (including worsening of laboratory values [e.g. new or worsening hypercalcemia]).
- No decline in ECOG performance status that can be attributed to disease progression.
- Absence of tumor progression at critical anatomical sites (e.g. leptomeningeal disease) that cannot be managed by protocol-allowed medical interventions.

Treatment beyond initial RECIST v1.1-defined progression is permitted only for patients who are clinically stable to continue on treatment until next imaging assessment (\geq 4 weeks later); this next imaging assessment should be no longer than 8 weeks later, to ensure that patients remain fit for salvage therapies. A longer time frame before the next assessment might be reasonable if no effective salvage therapies are available.

In addition, treatment beyond progression should not delay an imminent intervention to prevent serious complications of disease progression (e.g. central nervous system [CNS] metastases).

Patients for whom radiographic disease progression is confirmed at a subsequent tumor assessment may be considered for continuing study treatment at the discretion of the investigator if they still meet the criteria above and in absence of unacceptable toxicity.

23 MAY 2023 Version 6.0 Page: 114 of 181

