10.3.3 Efficacy variables

All efficacy variables evaluated using the RECIST v1.1 (see Appendix 16.2) are linked to the secondary objective of the study Part A (see Section 4). All variables evaluated using the iRECIST v1.1 (see Appendix 16.2) are exploratory only.

Efficacy data will be summarized using descriptive statistics and will be graphically displayed if appropriate. The correlation between pharmacodynamic parameters and selected safety, efficacy, or PK parameters may be graphically displayed. Further statistical analyses may be conducted.

23 MAY 2023 Version 6.0 Page: 137 of 181

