All other lesions (or sites of disease) including pathological lymph nodes (with short axis ≥ 10 mm and < 15 mm) should be identified as non-target lesions and should also be recorded at baseline. Measurements are not required and these lesions should be followed as 'present', 'absent', or in rare cases 'unequivocal progression' (more details to follow). In addition, it is possible to record multiple non-target lesions involving the same organ as a single item on the case record form (e.g. 'multiple enlarged pelvic lymph nodes' or 'multiple liver metastases').

Best Response: The best overall response is the best response recorded from the start of the study treatment until the end of treatment. The patient's best overall response assignment will depend on the findings of both target and non-target disease and will also take into consideration the appearance of new lesions. While some non-target lesions may actually be measurable, they need not be measured and instead should be assessed only qualitatively at the time points specified in the protocol.

Complete Response (CR): Disappearance of all target lesions. Disappearance of all non-target lesions and normalization of tumor marker level. Any pathological lymph nodes (whether target or non-target) must have decreased in size to have a short axis of ≤ 10 mm.

Partial Response (PR): At least a 30% decrease in the sum of diameters of target lesions taking as reference the baseline sum diameters.

Stable Disease (SD): Neither sufficient shrinkage to qualify for PR nor sufficient increase to qualify for PD, taking as reference the smallest sum diameters while on study.

23 MAY 2023 Version 6.0 Page: 175 of 181

Non-CR/Non-PD (to be used for patients with non-target lesions only): Persistence of one or more non-target lesion(s) and/or maintenance of tumor marker level above the normal limits.

Progressive Disease (PD): At least a 20% increase in the sum of diameters of target lesions, taking as reference the smallest sum on study (this includes the baseline sum if that is the smallest on study). In addition to the relative increase of 20%, the sum must also demonstrate an absolute increase of at least 5 mm. For non-target lesions, unequivocal progression (see comments below) of existing lesions represents progressive disease. (Note: the appearance of one or more new lesions is also considered progression).

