Resolution of iUPD

Progression is considered not confirmed, and the overall response becomes iSD/iPR/iCR, if:

- None of the progression-confirming factors identified above occurs, AND
- The target lesion sum of diameters (initial target lesions) does show a decrease beyond the initial PD threshold

The response is classified as iSD (decrease of SOD < 30 % from baseline and increase < 20% from nadir) or iPR (decrease of SOD \geq 30% from baseline) compared to baseline, or iCR if all lesions resolve.

In this case, the initial iUPD is considered to be pseudoprogression, and the level of suspicion for progression is "reset". This means that the next visit that shows radiographic progression, whenever it occurs, is again classified as iUPD by iRECIST, and the confirmation process is repeated before a response of iCPD can be assigned.

Management Following the Confirmatory Imaging

If repeat imaging does not confirm PD per iRECIST, as assessed by the investigator, and the patient continues to be clinically stable, study treatment may continue and follow the regular imaging schedule. If PD per iRECIST is assessed by the investigator, patients will be discontinued from study treatment.

Note: If a patient has confirmed radiographic progression (iCPD) as defined above, but the patient is achieving a clinically meaningful benefit, an exception to continue study treatment may be considered following consultation with the Sponsor. In this case, if study treatment is continued, tumor imaging should continue to be performed following the intervals as originally planned and submitted to the central imaging vendor.

Detection of Progression at Visits after Pseudoprogression Resolves

After resolution of pseudoprogression and tumor shrinkage (i.e., achievement of iSD/iPR/iCR), the bar is reset again and iUPD is indicated by any of the following events:

- Target lesions
 - o Sum of diameters reaches the PD threshold (≥20% and ≥5 mm increase from nadir) either for the first time, or after resolution of previous pseudoprogression. The nadir is always the smallest sum of diameters seen during the entire trial, either before or after an instance of pseudoprogression.
- Non-target lesions
 - o If non-target lesions have never shown unequivocal progression, their doing so for the first time results in iUPD.
 - If non-target lesions have shown previous unequivocal progression, and this
 progression has not resolved, iUPD results from any obvious further growth of

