6.2 Efficacy

Efficacy analyses will be performed on the EFS, unless otherwise specified.

All efficacy variables evaluated using the Response Evaluation Criteria in Solid Tumors (RECIST) version 1.1 are linked to the secondary and exploratory objectives of the study Part A. All variables evaluated using the Response Evaluation Criteria in Solid Tumors Modified for Immune-based Therapeutics (iRECIST) version 1.1 are exploratory only.

Efficacy data will be summarized using descriptive statistics and will be graphically displayed if appropriate. The correlation between pharmacodynamic parameters and selected safety, efficacy, or PK parameters may be graphically displayed. Further statistical analyses may be conducted.

Response as defined by RECIST version 1.1: complete response (CR), partial response (PR), stable disease (SD), progressive disease (PD). Response and progression will be evaluated in this trial using the new international criteria proposed by the RECIST committee for solid tumor.

iRECIST defines new response categories, including iUPD (unconfirmed progressive disease) and iCPD (confirmed progressive disease). For purposes of iRECIST assessment, the first visit showing progression according to RECIST 1.1 will be assigned a visit (overall) response of iUPD, regardless of which factors caused the progression.

Best overall tumor response according to RECIST criteria will be summarized using frequency counts. Best % change in Target Lesion sum of diameter from baseline will be displayed graphically for all subjects from worst to best in a waterfall plot.

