6.2.3 Exploratory Efficacy Variables

Exploratory efficacy variables defined according to RECIST version 1.1 will include disease control rate (DCR), duration of response (DOR), progression-free survival (PFS) (according to both RECIST and iRECIST), time to progression (TPP), time to response (TTR), overall survival (OS) and follow-up time.

These variables are defined as below:

Follow-up time is defined as the time from the date of first study treatment until death or the date of last contact, if the subject is still alive at the time of analysis.

Disease control rate (DCR) is defined as the percentage of subjects whose overall best response was not progressive disease (i.e. CR, PR, SD or Non CR/Non PD). Tumor assessments with SD as response, that is performed prematurely after assignment to treatment of the subject (i.e. substantially earlier than the first planned radiological tumor assessment at 9 weeks), will not be taken into account.

Duration of response (DOR) (for PR and CR) is defined as the time (days) from the first documented objective response of PR or CR, whichever is noted earlier, to disease progression or death (if death occurs before progression is documented). DOR will be defined for responders only, i.e. subjects with a CR or PR. The actual dates the tumor scans were performed will be used for this calculation. DOR for subjects who have not progressed or died at the time of analysis will be censored at the date of their last tumor assessment.

Kaplan-Meier (KM) product-limit estimates for median, 25th and 75th percentile with its 95% CI together with total number of subjects, total censored and total events will be provided for DOR per dose group. In addition KM survival curves will be presented for each dose group.

Progression-free survival (PFS) is defined as the time (days) from start of study treatment to date of first observed disease progression (investigator's radiological or clinical assessment) or death due to any cause, if death occurs before progression is documented. The actual date that the tumor scan was performed will be used for this calculation. If a tumor assessment is performed over more than one day (e.g. scans for chest and abdomen done on different days for the same evaluation), the earliest date will be used for the calculation of PFS. For subjects without documented radiological or clinical progression or death at the time of analysis, PFS will be censored at the last actual visit date of tumor evaluation.

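### RECIST 1.1 best response has no cut-off at first progression, so a partial response first seen after PD could count in ORR

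*Protocol*

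**What the plan says.** **Window.** Protocol Appendix 16.2, under Best Response: "The best overall response is the best response recorded from the start of the study treatment until the end of treatment". This is the only best-response window in either document.

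**Response.** The same appendix defines PR as "At least a 30% decrease in the sum of diameters of target lesions taking as reference the baseline sum diameters". Table 16–2 assigns the overall response at each visit from target lesions, non-target lesions and new lesions at that visit, without reference to an earlier PD.

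**ORR.** Protocol 10.3.3.1 and SAP 6.2.2 define ORR as the percentage of patients whose best response is CR or PR. Neither requires confirmation, and neither gives a cut-off date. SAP 6.2 adds only "Best overall tumor response according to RECIST criteria will be summarized using frequency counts".

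**Treatment past PD.** Protocol 7.4.4: "study treatment may continue beyond radiological progression as defined by RECIST v1.1", at the investigator's discretion. Protocol 9.4: "Treatment beyond initial RECIST v1.1-defined progression is permitted only for patients who are clinically stable". Protocol 6.4.1.3 allows treatment to be considered even after PD is confirmed on a later scan.

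**iRECIST.** Appendix 16.2 labels the first RECIST 1.1 PD visit iUPD. If it reverses, "Progression is considered not confirmed, and the overall response becomes iSD/iPR/iCR". Protocol 10.3.3: "All variables evaluated using the iRECIST v1.1 (see Appendix 16.2) are exploratory only". SAP 6.2.3 names one variable under both criteria: "progression-free survival (PFS) (according to both RECIST and iRECIST").

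**PFS and TTP.** Protocol 10.3.3.2 (PFS) and SAP 6.2.3 (PFS and time to progression) end at the first observed progression.

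**The concern.** ORR and PFS are both labelled RECIST 1.1 but stop at different points. PFS stops at first progression. Best response stops at end of treatment, which in this trial can fall well after progression. Scans taken after PD in patients who stay on treatment are therefore inside the best-response window, and one unconfirmed PR on such a scan is enough.

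A single patient could then be progressed for PFS and TTP, and later become a responder for ORR, under the same criteria. Time to response would exceed PFS for that patient. ORR is the only secondary efficacy variable, so its derivation should not depend on whether a programmer follows the appendix literally or follows the apparent intent of the iRECIST section.

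**Working it through.** **1. The plan's own figure.** Protocol 10.4 bases 26 evaluable patients on Jeffreys priors, Beta(0.5, 0.5), and a response rate of 0.4. With posterior Beta(0.5 + x, 26.5 − x):

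- x ≥ 14 of 26: P(π > 0.4) = 0.924 at x = 14, and power 0.801 at π = 0.6.
- x ≤ 7 of 26: P(π ≤ 0.4) = 0.916 at x = 7, and power 0.968 at π = 0.15.

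These match the stated 92%/80% and 91%/96%. The point below does not alter them. They confirm 26 as the denominator to use.

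**2. Can a post-PD PR fall inside the window?** An assumed patient has one set of target lesions, no new lesions, no non-target PD, stays on treatment and is clinically stable:

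| Scan | Sum (mm) | Change | RECIST 1.1 visit response | iRECIST |
|---|---|---|---|---|
| Baseline | 100 | – | – | – |
| Week 9 | 122 | 122/100 − 1 = +22%, +22 mm from the smallest sum | PD (at least 20% and 5 mm) | iUPD |
| Week 15 | 68 | 68/100 − 1 = −32% from baseline | PR (Table 16–2) | iPR |

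The week 15 scan is 6 weeks after week 9, inside the 4 to 8 weeks that Appendix 16.2 gives for repeat imaging.

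**3. Endpoints for this patient, read literally.**

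- PFS and TTP: event at 9 × 7 = 63 days.
- Best response: PR, because week 15 precedes end of treatment. The patient counts in ORR.
- Time to response: 15 × 7 = 105 days, which is 42 days after the PFS event.

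**4. How narrow is the route?** All of the following are needed:

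- PD came from target lesions, or any new lesion or non-target PD is no longer present at the later visit. Otherwise Table 16–2 keeps that visit at PD.
- The sum falls at least 30% below baseline, not merely below the PD scan.
- Treatment continued past PD.
- PD was recorded. Protocol 9.4 lets the investigator postpone the PD diagnosis to the next scan when its clinical criteria are met. If that was done at week 9, week 15 may be an ordinary first PR with no conflict.

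**5. Size.** The documents give no count of such patients, and it may be zero. Per affected patient, ORR rises by 1/26 = 3.8 points, 1/30 = 3.3 points or 1/50 = 2.0 points at the three sample sizes in the protocol.

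**6. End-of-treatment scan.** Protocol 9.2.2.5 places it within 14 days after permanent discontinuation. Appendix 16.2 does not say whether a scan in that interval falls inside a window that closes at end of treatment.

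**The case against.** The strongest reply is that the structure of Appendix 16.2 already separates the two. There is no distinct iRECIST assessment until RECIST 1.1 PD. From that visit on, outcomes carry the i prefix, and Protocol 10.3.3 makes iRECIST variables exploratory. On that reading the week 15 scan is an iPR and never reaches RECIST ORR. The appendix also refers to an Imaging Manual, not among the documents reviewed, which may contain the rule. This is probably the intent, and it is why the point is minor. But the appendix states its own RECIST 1.1 window, and no sentence in either document excludes a visit PR after PD from it. A programmer who follows the written rule includes it.

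Some stronger readings are tempting but not supported:

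- **Responses first seen after stopping treatment are wrongly lost.** Limiting best response to the treatment period is a defensible choice. The synopsis says patients who stop without PD are followed for progression. Only the silence on the end-of-treatment scan needs repair.
- **The window runs on into new anti-cancer therapy.** Protocol 6.4.1.3 requires withdrawal from study treatment when other anti-cancer therapy is used, so the window closes at about that time.
- **Duration of response becomes undefined.** It runs from the response, so the natural end is the next PD. If the sum in the example rose to 82 mm at week 27 (82/68 − 1 = +21%, +14 mm), duration would be (27 − 15) × 7 = 84 days.
- **An iRECIST best-response table is missing.** No objective calls for one, and SAP 6.2 leaves room for further analyses.

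**Conclusion.** The point holds as a minor gap in definition. Followed literally, the RECIST 1.1 best-response rule can make a patient a responder after a recorded RECIST PD, so ORR and PFS can disagree for that patient. Each such patient adds 3.8 points to ORR at 26 patients.

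This rests on reading the Appendix 16.2 window as written, on PD having been recorded rather than postponed, and on no contrary rule in the Imaging Manual.

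A reader might infer that ORR is biased upward by a known amount, or that a go/no-go decision is at risk. The documents support neither. They give no frequency, so no total effect or plausible range can be stated. One extra responder would move P(π > 0.4) from 0.851 at 13 of 26 to 0.924 at 14 of 26, but the Bayesian thresholds appear only in the sample-size rationale of Protocol 10.4 and are not decision rules. Protocol 10.1 and SAP 4.1 describe the analysis as exploratory, with nothing confirmatory.

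**What to change.** Add to Protocol Appendix 16.2 and SAP 6.2:

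*RECIST 1.1 best overall response, and hence ORR, DOR and TTR, uses only assessments up to and including the first RECIST 1.1 PD; responses first seen after that PD are reported under iRECIST only.*

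In the same place, state whether the end-of-treatment scan, and follow-up scans before PD and before new systemic therapy, count towards best response. Either choice is acceptable if it is stated.

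Protocol 5.2.3 plans no further analysis after primary completion, so the analysis may already have been run. In that case, do not redefine the endpoint afterwards. State in the study report which rule was used, and list any patient whose first response followed RECIST 1.1 PD.

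The cost is wording and a little derivation code. No new data are needed, and the rules on continuing treatment are untouched. ORR may be slightly lower than under the literal window.

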consultation with the sponsor. The use of inhaled corticosteroids, physiologic replacement doses of glucocorticoids and mineralocorticoids (e.g. fludrocortisone) for patients with orthostatic hypotension or adrenocortical insufficiency is allowed. Megestrol administered as an appetite stimulant is acceptable while the patient is enrolled in the study.

- Influenza vaccination should be given during influenza season only (approximately October to March in most regions). Patients must not receive live, attenuated influenza vaccine within 28 days prior to start of study treatment, during treatment, or within 90 days following the last dose of atezolizumab. Patients may receive inactivated vaccines.
- COVID-19 vaccines are allowed during study treatment. Vaccines based on mRNA technology are preferred, but also live, attenuated vaccines can be allowed if deemed appropriate for cancer patients.
- Patients taking narrow therapeutic index medications should be monitored proactively as per local standard of care.
- Antiemetic therapy is allowed.
- Bisphosphonates or denosumab with supplement of calcium and vitamin D.
- Treatment with "non-conventional therapies" (such as acupuncture), and vitamin / mineral supplements are permitted provided that they do not interfere with the study endpoints, in the opinion of the investigator (to be documented in the source notes and in the eCRF).
- Palliative radiotherapy for pain control (e.g. treatment of known bony metastases). Radiotherapy to target lesions is not allowed.

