Until radiographic disease progression based on RECIST 1.1, there is no distinct iRECIST assessment.

Assessment and Decision at RECIST 1.1 Progression

For patients who show evidence of radiological PD by RECIST 1.1 the investigator will decide whether to continue a patient on study treatment until repeat imaging is obtained (using iRECIST for patient management). This decision by the investigator should be based on the patient's overall clinical condition and agreement.

Clinical stability is defined as the following:

- Absence of symptoms and signs indicating clinically significant progression of disease
- No decline in ECOG performance status
- No requirements for intensified management, including increased analgesia, radiation, or other palliative care

For any patient deemed **clinically unstable** the investigator should discontinue the study treatment.

If the investigator decides to continue treatment, the patient may continue to receive study treatment and the tumor assessment should be repeated 4 to 8 weeks later to confirm or reject PD by iRECIST and to ensure that patients remain fit for salvage therapies.

Tumor flare may manifest as any factor causing radiographic progression per RECIST 1.1, including:

- Increase in the sum of diameters of target lesion(s) identified at baseline to ≥20% and >5 mm from nadir
 - Note: the iRECIST publication uses the terminology "sum of measurements", but "sum of diameters" (SOD) will be used in this protocol, consistent with the original RECIST 1.1 terminology.
- Unequivocal progression of non-target lesion(s) identified at baseline
- Development of new lesion(s)

iRECIST defines new response categories, including iUPD (unconfirmed progressive disease) and iCPD (confirmed progressive disease). For purposes of iRECIST assessment, the first visit showing progression according to RECIST 1.1 will be assigned a visit (overall) response of iUPD, regardless of which factors caused the progression.

At this visit, target and non-target lesions identified at baseline by RECIST 1.1 will be assessed as usual.

23 MAY 2023 Version 6.0 Page: 178 of 181

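### Protocol Sections 6.4.1.3 and 9.4 and Appendix 16.2 set inconsistent conditions for continuing study treatment after RECIST 1.1 progression

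*Protocol*

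**What the plan says.** Section 6.4.1.3 places RECIST 1.1 progression among the reasons for which a patient may, not must, be withdrawn. It permits continuation if four conditions all hold: clinical benefit, no signs of unequivocal progression, no ECOG decline due to progression, and no unmanageable progression at critical anatomical sites. Section 9.4 repeats the four conditions; its ECOG item reads "No decline in ECOG performance status that can be attributed to disease progression". Both sections then say that patients with confirmed progression "may be considered for continuing study treatment at the discretion of the investigator if they still meet the criteria above". Neither mentions the sponsor at that step.

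Appendix 16.2 sets its own test. Clinical stability requires no clinically significant signs of progression, "No decline in ECOG performance status", and "No requirements for intensified management, including increased analgesia, radiation, or other palliative care". For a clinically unstable patient, "the investigator should discontinue the study treatment". Once progression is confirmed by iRECIST, the appendix directs discontinuation. If the patient has meaningful clinical benefit, "an exception to continue study treatment may be considered following consultation with the Sponsor".

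**The concern.** All three places govern one decision: whether a patient stays on rogaratinib and atezolizumab after a scan meets RECIST 1.1 progression. The appendix is not merely background, because Section 9.4 says that iRECIST supports the determination of progression for treatment decisions. An investigator who reads only 6.4.1.3 or 9.4, and one who reads only the appendix, can reach different decisions for the same patient, and each can point to protocol text. The stake is first of all patient management. After that comes treatment duration, which SAP Section 6.4 summarises, and possibly iRECIST PFS (SAP Section 6.2.3), because unconfirmed progression becomes confirmed or resolves only on a further scan.

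**Working it through.** The plan gives no figure on this point, so the check is a comparison of the current text.

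| Item | Sections 6.4.1.3 and 9.4 | Appendix 16.2 | Same? |
|---|---|---|---|
| Confirmed progression | Investigator's discretion, if the four conditions still hold | Discontinue; exception after consulting the sponsor | No: default and decision step both differ |
| ECOG decline | Only a decline attributable to progression counts | Any decline counts | No |
| More analgesia, radiation or palliative care | Not listed | Listed as instability | No |
| Critical anatomical sites | Listed | Not listed | No |
| Repeat scan | 9.4: 4 to 8 weeks, longer if no effective salvage therapy; also, diagnosis of progression may be postponed to the next study evaluation | 4 to 8 weeks, no extension | Core window shared; the rest differs |

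Two cases show the main conflicts.

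1. Progression is confirmed and the four conditions still hold. Under 6.4.1.3 and 9.4 the investigator may continue treatment alone. Under 16.2 the patient stops unless the sponsor has been consulted about an exception.
2. Progression is unconfirmed, and ECOG falls from 0 to 1 because of an intercurrent illness. The ECOG condition in 6.4.1.3 and 9.4 is met. The stability definition in 16.2 is not, and the instruction there is to discontinue.

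The only arithmetic concerns the repeat scan. Section 9.4 says that "this next imaging assessment should be no longer than 8 weeks later". The regular interval there is 9 weeks ± 7 days:

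- earliest 9 − 1 = 8 weeks, latest 9 + 1 = 10 weeks, counted from a progression scan on its nominal day;
- so a routine next scan meets the 8-week limit only at the early edge of its window.

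Hence postponing to the next study evaluation, if that means the next routine scan, does not fit the 4 to 8 weeks stated elsewhere in 9.4 and in 16.2.

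**The case against.** The strongest reply is that nothing in 6.4.1.3 or 9.4 tells anyone to continue. Both only permit it, so a site that stops a patient under 16.2 breaches neither. Section 9.4 also limits treatment beyond progression to patients who are *clinically stable*, does not define the term, and refers to Appendix 16.2 for iRECIST. The appendix can then be read as supplying the definition, which softens the ECOG and palliative-care differences. Finally, 16.2 asks for consultation, not approval, so the outcome after confirmed progression may often be the same.

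Much of this stands, and it rules out several stronger readings.

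- *Opposite stopping instructions.* A reader might infer these, but the conflict is between a permission and a direction to stop.
- *A contradiction with Section 8.1.* That section allows palliative radiotherapy for pain as general concomitant therapy and does not address treatment after progression. A patient newly needing it may also fail the clinical-benefit condition in 6.4.1.3 and 9.4, which asks for stable or improved symptoms.
- *Repeat scans of up to 16 weeks.* This takes the interval after primary completion (14 + 2 = 16 weeks) and reads the postponement wording as the next routine scan. Section 9.4 allows a scan at any time if progression is suspected. The appendix's own example puts a confirmatory scan at week 13 between scans at weeks 9 and 18, that is 13 − 9 = 4 weeks later.

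Two conflicts survive. Reading the texts together does not reconcile investigator discretion with a default of discontinuation and a sponsor step. Nor does it explain why 6.4.1.3 and 9.4 attach a cause to the ECOG decline while 16.2 does not.

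**Conclusion.** The inconsistency is real and is in the current text. It rests mainly on the decision after confirmed progression and on ECOG decline; palliative measures, critical anatomical sites and repeat-scan timing are secondary. The conclusion assumes that confirmed progression in 6.4.1.3 and 9.4 is the same event as confirmed progression under iRECIST in 16.2. Section 9.4's use of iRECIST for treatment decisions supports that assumption.

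The size is modest. The effect is on consistency of management and on treatment duration, with a possible effect on iRECIST PFS. The number of patients affected is not given.

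A reader might go further and infer damage to the main results. The documents do not support that:

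- DLTs are counted in the first 21 days, and the first on-treatment scan is no earlier than 9 weeks (9 × 7 = 63 days).
- RECIST PFS is dated at first observed progression; no effect on it is claimed.
- Variables evaluated by iRECIST are exploratory only (Protocol Section 10.3.3, SAP Section 6.2), and the trial is single-arm with no confirmatory analysis.
- The 14-week schedule applies only after primary completion, when Section 5.2.3 plans no further analysis.
- That sites actually applied different rules is an inference; the documents only make it possible.

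**What to change.** Reconcile Sections 6.4.1.3 and 9.4 and Appendix 16.2 into one list of conditions for treatment beyond RECIST 1.1 progression, kept in one place and cross-referenced from the others. It should contain:

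- one statement on ECOG decline, saying whether cause matters;
- one statement on palliative measures, worded so that it can be read alongside Section 8.1;
- one statement on critical anatomical sites;
- one statement on who decides after confirmed progression, and whether the sponsor is consulted;
- one repeat-scan window, saying whether any extension applies, in place of the reference to the next study evaluation;
- a definition of *clinically stable*, if the term is kept.

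Which rule applies in each case is for the sponsor to decide.

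The cost is protocol wording only. No visit is added, because 9.4 and 16.2 already call for the repeat scan. The benefit is to patients still on treatment; rewording cannot change data already analysed.
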